
Background and Significance:

Affecting as many as 1 in 88 children (1 in 58 boys) in the United States, ASD is an increasingly common childhood neurobiological condition.¹-⁵ Anxiety disorders are common and impairing among children with ASD. As many as 50% of youth with ASD have ≥1 diagnosable anxiety disorder. Generalized anxiety disorder affects at least 35% of those with ASD; separation anxiety disorder affects at least 38%; obsessive-compulsive disorder (OCD) affects at least 37%; and social phobia affects at least 30%.⁶⁻⁹ Clinically significant anxiety is associated with functional impairment and poor outcomes in youth with ASD.¹0-13 The relative frequency of clinical anxiety among children with ASD indicates that anxiety is an important treatment focus,¹4,15 with parents rating it as the second biggest problem for youth with ASD.¹6

Clinical anxiety is linked with significant functional impairment in youth with ASD. For example, higher parent-rated child anxiety is associated with greater impairments in social responsiveness¹¹ and social skills¹⁰ in youth with ASD. This follows from the tendency of social anxiety to promote social avoidance, which prevents opportunities for the development of relationships.¹⁷⁻¹⁹ In individuals who already have social skill deficits, social avoidance likely adds an additional barrier to friendship and acceptance.

1 | P a g e

Additionally, several large studies of children with ASD have found strong linkages between clinical anxiety and increased severity of ASD symptoms, such as repetitive behaviors¹¹, sensory symptoms²⁰, and total ASD symptoms,²¹ even when controlling for intellectual impairment, social maladjustment, and degree of speech impairment. It is therefore possible that treatment of anxiety could positively impact core ASD symptom severity.²²

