Repetitive behaviors can interfere with the development of positive peer relations.⁶⁴ Circumscribed interests and stereotypies associated with ASD may prevent children from experiencing rewarding peer interactions because they engender rejection. Standard CBT interventions do not address these symptoms. However, habit reversal⁶⁵ and operant procedures⁶⁶ are promising techniques that we have adapted to reduce manifestations of circumscribed interests and stereotypies during peer interactions.^{58, 60, 63}

Moderators of treatment effects help answer the question "What treatment works best for which patient?" ⁶⁷ Kraemer has argued that clinical trials primarily powered to test treatment efficacy can play an important role in generating hypotheses about patient subgroups that may respond better to specific treatment modalities. ^{68, 69} Moderator variables are initially based on empirical precedent, theory, and logic. A number of pediatric clinical trials for depression have found that baseline symptom severity moderates outcome (e.g., ^{70, 71}). In a recent study, Puleo and Kendall⁴⁰ found that autism symptom severity in typically developing children moderated treatment response in standard CBT versus family-based CBT. A similar relationship is expected in the present trial. For example, greater ASD symptom severity (e.g., social communication impairments) may be a hindrance to optimal response to standard CBT. In comparison, personalized CBT for anxiety in ASD (BIACA) uses ASD-specific adaptations and collateral supports to overcome ASD-related challenges. Thus, the more prominent a child's ASD symptoms, the more we expect BIACA to differentially impact treatment outcome in comparison to standard CBT.

The present trial will explore mediation. 68 This trial recognizes a synergy between anxiety and autism symptoms in children with ASD. Therefore, it is of considerable importance to explore whether treatment-related reductions in anxiety mediate improved autism symptoms, and, complementarily, whether treatment-related reductions in autism symptoms mediate improved anxiety. Because anxiety is considered both a product of autism-related stress (e.g., social confusion) as well as a trigger of exacerbated autism symptoms that serve as a maladaptive coping response (e.g., social isolation, repetitive behaviors), 32, 40 it follows that improvements in the affect domain might beget improvement in autism symptom severity, and vice versa.

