The considerable mental health need among children with ASD and clinically distressing anxiety is a widespread problem in need of attention. The proposed project advances the field by providing a rigorous test of efficacy of personalized CBT for anxiety in ASD against standard practice CBT for anxiety by addressing the following: (1) The study will be adequately powered to test the primary and secondary hypotheses. By employing a condition that represents standard CBT (i.e., Coping Cat), the study will answer the question of whether CBT personalized to the needs of youth with ASD and anxiety outperforms standard CBT.^{72, 73} (2) The trial will include multi-method outcome measurement, including measures of anxiety valid in ASD samples, and measures of functioning independent of anxiety severity.

(3) An a priori moderator will be tested, and other moderators will be explored. (4) A multisite plan, with therapy supervision provided by study personnel other than PIs/treatment developers, provides information on the portability of treatment and enhances generalizability of findings.

Specific Aims:

- Aim 1: To evaluate differential change over time in anxiety symptoms and response rates for the treatment conditions compared to each other and relative to a treatment as usual (TAU) control group.
- Aim 2: To examine the durability of treatment gains for youth who are deemed as treatment responders.
- Aim 3: To identify patient factors that are linked with differential treatment response such as the interaction between treatment condition and ASD severity on outcome measures post-treatment.
- Aim 4: To explore whether treatment reductions in anxiety mediate improved autism symptoms and whether treatment related reductions in autism symptoms mediate improved anxiety

Research Plan:

Overview

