Specific Analyses for the Individual Study Aims: Aims 1-2: For Primary Aim 1, to model anxiety symptoms, we will use the PARS as the dependent measure in a mixed effects regression with condition as the betweensubject factor, time (Screening, Mid-treatment, Post-Treatment) as the within-subject factor and a Condition x Time interaction, with the latter used as evidence for differential rates of change. For the dichotomous outcome, treatment response (Aim 2), we will also use mixed effects regression, this time with a logistic link, with treatment condition, time (here Mid-treatment and Post-Treatment), and a Condition x Time interaction. Our primary interest is in the contrast at the end of acute treatment. The relevant continuous assessment measures for Aim 2 are described in detail in section C.5. (e.g., POPE, SRS); these scales will be assessed with the same model as in Aim 1. Aim 3: For continuous outcomes, the models of Aims 1-2 will be refit for responders only, adding the 6-month follow-up time point. Within-subjects contrasts between the follow-up time point and screening will allow us to test whether and when subjects remain significantly improved post-treatment. Evidence of deterioration (e.g., increased symptoms) over the follow-up period will also be of interest. Since all subjects in this analysis are by definition responders at treatment conclusion, we will use mixed effects logistic regression to model the likelihood of relapse or recurrence over the follow-up period. We will also report the proportions of subjects within each treatment arm who ever relapse or experience recurrence. Aim 4: To examine moderation, the interaction term between treatment condition and ASD severity will be used to examine changes over time for the continuous (PARS scores) and categorical outcomes (responder status; CGI-I). Significant interactions will be followed up by stratifying on treatment condition and examining parameter estimates, with 95% CI, for ASD severity and the outcomes. Exploratory Aim 5: Testing the mediation hypothesis requires that the direct path is meaningfully attenuated when the mediator is in the model and is also a significant predictor

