of outcome. Significant effects yielded in tests of Aims 1-2 will be further evaluated by including the midtreatment mediator variables specified in B.2 in separate linear regression models and will employ bootstrapped estimates of the indirect effects.¹⁴¹ Aim 6: The same analytic plan for tests of moderation will be applied with select potential moderators.

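### The exploratory mediation models name no Screening or Mid-treatment adjustment, so separate treatment effects on correlated anxiety and autism measures can be reported as mediation

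*Combined protocol and SAP*

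**What the plan says.** The whole mediation plan stands in Analytic Design, Specific Analyses for the Individual Study Aims, under Exploratory Aim 5. (The Specific Aims list has the same question as Aim 4.)

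- **Criterion.** "Testing the mediation hypothesis requires that the direct path is meaningfully attenuated when the mediator is in the model and is also a significant predictor".
- **Model.** Effects found significant for Aims 1-2 "will be further evaluated by including the midtreatment mediator variables specified in B.2 in separate linear regression models".
- **Inference.** The models "will employ bootstrapped estimates of the indirect effects".

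No covariate is listed. Section B.2, which is cited for the mediators, is not part of this document. The general paragraph that opens Analytic Design says that the mixed models can control for confounders. It names no variable and does not refer to the mediation regressions.

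The question itself is two-directional and about change. Background and Significance asks "whether treatment-related reductions in anxiety mediate improved autism symptoms, and, complementarily, whether treatment-related reductions in autism symptoms mediate improved anxiety".

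On how closely the two domains are related, the documents point two ways. Background and Significance says that several large studies "have found strong linkages between clinical anxiety and increased severity of ASD symptoms". Assessments and Measures says that the anxiety measures were chosen partly because they show negligible correlation with autism severity measures. Neither place gives a coefficient.

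**The concern.** The Aim 1 mixed model carries Screening as a level of time. A separate linear regression of the Post outcome on arm and the Mid mediator does not, unless the Screening values are added by name.

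Suppose treatment lowers anxiety and, by a separate route, lowers autism severity, and that the two are correlated across children. Within each arm, a child who is high on the mediator at Mid tends to be high on the outcome at Post simply because of that shared level. The mediator coefficient is then non-zero. Because treatment also moved the mediator, the indirect effect is non-zero and the direct path shrinks. Both stated criteria can be met with no path from mediator to outcome. The same holds with mediator and outcome exchanged.

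At stake is the exploratory claim that reducing anxiety improves autism symptoms, or the reverse. The trial could report either or both when treatment merely moved two related measures independently.

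**Working it through.** **Inputs from Power Analyses and Sample Size Considerations:** 81 per CBT arm at the end of acute treatment, two-sided α = .05, r = .5 between visits, and d = .44 as the difference detectable with 80% power at one acute time point.

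**Assumptions, because the documents give no figure:** the correlation between the constructs, and the size of the treatment effect on each of them at Mid.

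**Step 1: the plan's own figure.** SE of an arm difference = √(2/81) = .157. Then .44/.157 = 2.80, and power = Φ(2.80 − 1.96) = Φ(.84) = .80. The stated 80% is reproduced.

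**Step 2: data with no mediation.** Each construct at each visit is a stable trait plus a visit-specific state, each with variance .5, which gives r = .5 between visits. Traits correlate at ρ across constructs. States at the same visit correlate at .3 (at .1 in the ρ = .1 row below). There is no path from one construct to the other.

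**Step 3: the spurious coefficient.** With arm in the model and nothing else, the coefficient of the Mid mediator is b = .5 × ρ: .15 at ρ = .3 and .25 at ρ = .5. With a = c = .44, the direct path c − a·b becomes .44 − .44 × .15 = .374 (15% attenuation) or .44 − .44 × .25 = .33 (25%).

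**Step 4: how often this is declared mediation.** A hand approximation multiplies the chance that a is significant by the chance that b is, with SE(b) ≈ √((1 − b²)/162).

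- For a: .80 at d = .44. At d = .22, .22/.157 = 1.40 and Φ(−.56) = .29. With no effect, .05.
- For b = .15: SE .0777, z = 1.93, chance .49.
- For b = .25: SE .0761, z = 3.29, chance .91.
- For b = .05 (ρ = .1): SE .0785, z = .64, chance .10 (both tails).

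The simulated column gives the share of trials, per direction, in which the bootstrap interval excluded zero. Ranges are across independent runs.

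| Setting | By hand | Simulated |
|---|---|---|
| ρ = .3, d = .44 at Mid | .80 × .49 = 39% | 38% to 40% |
| ρ = .5, d = .44 at Mid | .80 × .91 = 73% | 73% to 74% |
| ρ = .3, d = .22 at Mid | .29 × .49 = 14% | 12% to 13% |
| ρ = .1, d = .44 at Mid | .80 × .10 = 8% | 7% to 9% |
| ρ = .3, no effect on mediator | .05 × .49 = 2% | about 2% |

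**Step 5: adding covariates (d = .44 at Mid and Post).** With Screening values of mediator and outcome, the rate falls to 21% to 22% at ρ = .3 and 37% to 38% at ρ = .5. With the Mid outcome added as well, it is 4% to 6%.

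**Step 6: other data models.** Both have a Mid-to-Post cross-correlation of .30 and d = .44 at Mid and Post.

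| Model | Covariates | Per direction | Both directions |
|---|---|---|---|
| Traits correlated .6, states uncorrelated | none | 78% to 79% | 63% |
| | Screening | 27% to 28% | 9% |
| | Screening + Mid outcome | 17% | 4% |
| First-order autoregressive, same-visit correlation .6 | none | 77% | 65% |
| | Screening | 82% | 71% |
| | Screening + Mid outcome | 4% to 5% | 0.4% |

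With d = .22 at Mid, the unadjusted rates in these two models are 28% to 31% per direction and 12% to 17% in both. With no treatment effect on either construct they are about 5% per direction.

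**The case against.** The case on the other side has several parts.

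- **Correlation alone is harmless.** A reader might infer that the shared level of anxiety and autism severity is enough to produce mediation findings. It is not: the indirect effect is a product, and with no treatment effect on the mediator the rate stays at or near nominal. This stands and limits the point.
- **The correlation may be small.** The measure-selection statement about negligible correlations favours the bottom of the range, and the background statement favours the top. This stands; the documents do not decide it.
- **The omission is read from silence.** The plan does not exclude Screening values, and section B.2 is not available. The aim speaks of reductions, so a change-score mediator is a fair reading. On that reading the rate was 4% to 5% per direction under the stable-trait model, but 36% to 38% (18% in both directions) under the autoregressive one. The objection stands in part, since a change score does not reliably cure the problem.
- **The significance gate helps.** Only outcomes with a significant Aim 1-2 effect go forward. Applying such a gate in the ρ = .3, d = .44 case lowered the rate from 40% to 33%, with 14% in both directions. It reduces the error but does not remove it, because the gate opens for both directions when treatment moves both constructs. The documents give no ground for calling the gate or the attenuation criterion faults.
- **The two hypotheses are complementary.** A reader might take a finding in both directions as self-contradictory. The protocol expects improvement in each domain to bring improvement in the other, so it is not. The difficulty is only that the unadjusted model can give that result when neither path exists.
- **The aim is exploratory.** This stands.

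**Conclusion.** The concern holds as a gap in the specification of an exploratory analysis. If the regressions are fitted as written, with the Mid mediator and no Screening or Mid covariates, independent treatment effects on two correlated constructs can be reported as mediation.

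The main estimate of about 39% to 74% per direction rests on an assumed trait correlation of .3 to .5 and on d = .44 for both constructs already at Mid. The plan gives .44 as a detectable difference at a single time point, not as an expected one. With half that effect at Mid the rate is about 13% at ρ = .3, and with correlation .1 it is near nominal.

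A reader might infer that the trial's efficacy conclusions are at risk. They are not: nothing in the primary analyses depends on these models. Nor do the documents show that the plan rejects baseline adjustment; they only fail to specify it.

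**What to change.** Add to Exploratory Aim 5:

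1. Every mediation model, for the mediator and for the outcome, includes the Screening values of both.
2. A directional claim also requires the Mid value of the outcome in the outcome model, fitted in both directions, wherever that value is measured. The ADOS-2 is scheduled only at screening and post, so this step is not available when it is the outcome.

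Step 1 also settles whether the mediator is a level or a change. Since b(M₁ − M₀) + cM₀ = bM₁ + (c − b)M₀, the mediator coefficient is the same either way once the Screening mediator is in the model. Step 1 is not sufficient alone, as the autoregressive results show.

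The cost is a few lines of SAP text, with no new visits or measures. Adjusting for the Mid outcome misses mediation already complete by Mid, so the estimate is conservative. Some bias can remain if a stable trait is measured with error (17% per direction in the least favourable adjusted case above), and the report should say so.

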
Missing Data and Attrition: Our primary analytic tool is GLMM, which provides unbiased parameter estimates when data are missing at random. GLMM estimates are based on maximum likelihood techniques and do not require imputation. Because the intermediate time points for subjects who do not complete the full protocol provide information about their trajectory, we feel this is more appropriate than LOCF, which assumes a flat trajectory. However, we recognize that if dropout that is differentially

associated with outcomes in a way not captured by the available trajectories (i.e., non-ignorable rather than MCAR/MAR), this could compromise treatment comparisons. We will attempt to identify possible sampling biases by performing multiple logistic regression analyses on dropout using measures of clinical status at screening or prior to dropout as covariates. If warranted, we will use imputation and propensity score approaches to handle bias problems. Every effort will be made to prevent dropouts/missing data, or to complete relevant assessments for patients who drop out.

12. References:

- 2. Fombonne E. Epidemiology of autistic disorder and other pervasive developmental disorders. *J Clin Psychiatry*. 2005;66 Suppl 10:3-8.
- 3. CDC. Prevalence of autism spectrum disorders--autism and developmental disabilities monitoring network, 14 sites, United States, 2002. *MMWR Surveill Summ.* 2007;56(1):12-28.
- **4.** (CDC) CfDCaP. Prevalence of the autism spectrum disorders-autism and developmental disabilities monitoring (ADDM) network. *MMWR Surveill Summ*. 2009;58(SS-10).
- 5. CDC. Prevalence of Autism Spectrum Disorders—Autism and Developmental Disabilities Monitoring Network, 14 Sites, United States, 2008. MMWR Surveill Summ. 2012;61:1-19.
